**Table 2.1-2: Blinded Dosing Schedule (Cycle 3+)**

1 Cycle = 14 Days = 2 weeks		
	C3D1	C3D8
Arm A (Nivo)	Nivo: 240mg (24mL diluted to 100mL)	
Arm B (Nivo + Ipi)	Nivo: 240mg (24mL diluted to 100mL)	
Arm C (Placebo)	Nivo pbo: 100mL	

## 2.2 Treatment Assignment

Subjects are enrolled using the Interactive Voice Response System (IVRS) to obtain a subject ID. Subjects who have signed informed consent and met all eligibility criteria will be ready to be randomized through the IVRS, upon confirmation of receipt of required tissue sample by the central lab. The following information is required for subject randomization:

- Subject number
- Date of birth
- Submission of tumor tissue sample to central lab
- ECOG Performance Status: 0 vs. 1
- Sex: Male vs. Female
- Prophylactic Cranial Irradiation (PCI) following chemotherapy: Yes vs. No

The IVRS will randomly assign the subject in a 1:1:1 ratio to either Arm A (nivolumab), Arm B (nivolumab/ ipilimumab), or Arm C (placebo), stratified by the following factors:

- ECOG Performance Status: 0 vs. 1
- Sex: Male vs. Female
- Prophylactic Cranial Irradiation (PCI) following chemotherapy: Yes vs. No

The randomization will be carried out via permuted blocks within each stratum.

## 2.3 Blinding and Unblinding

The subjects, investigator and site staff will be blinded to the study drug administered. Each investigative site must assign an unblinded pharmacist. An unblinded site monitor will be assigned by the Sponsor/or designee to provide oversight of drug supply and other unblinded study documentation. In the event of a medical emergency in an individual subject, the treating physician may be unblinded if knowledge of the investigational product is critical to the subject's management.

The Sponsor will remain blinded until final PFS results are unblinded following guidelines specified in the DMC Charter or until final analysis of the OS endpoint, whichever occurs first. The independent DMC will be unblinded to enable review of safety and efficacy reports. Details are specified in the DMC Charter

Designated staff of BMS Research & Development may be unblinded prior to database lock to facilitate bioanalytical analyses. A bioanalytical scientist in the Bioanalytical Sciences department (or designee in the external central bioanalytical laboratory) will be unblinded to the randomized treatment assignments in order to minimize unnecessary bioanalytical analysis of samples from control group subjects.

## 2.4 Protocol Amendments

**Table 2.4-1: Protocol Amendments**

Amendments	Date of issue	Summary of Major Changes
Revised Protocol 06	20-Sep-2018	
 
Moved OS of nivolumab vs placebo to secondary objectives
 
Updated sample size and power analysis
 

Revised Protocol 05	14-Jul-2018	
 
BICR-assessed PFS was changed from primary objective to secondary objective and the associated PFS analysis was removed
 
To evaluate Tumor mutational burden (TMB) as a potential predictive biomarker for efficacy was added as secondary objective
 
The number of events required for primary analysis of OS was changed from 576 events to 593 events
 

Revised Protocol 04	12-Sep-2017	
 
Details of tissue requirements updated
 
Maximum treatment duration added
 
Contraception language updated to program standards
 
Exclusion criteria added botanical preparations
 
Prohibited/restricted treatments updated
 
Dose modifications were updated to program standards
 
Immune-mediated adverse events description added
 
RECIST 1.1 updated as per BMS standards
 

Amendment 12 (site specific)	01-May-2017	
 
Add a China specific sub-study to allow enrollment of patients from China (~130 randomized subjects)
 

Revised Protocol 03(incorporates Amendment 11)	31-Aug-2016	
 
Extended the time to randomization and modified tissue requirements for eligibility. The period following last dose of chemotherapy has been extended from 7 to 9 weeks (and from 9 to 11 weeks if patients undergo PCI).
 

**Table 2.4-1: Protocol Amendments**

Amendments	Date of issue	Summary of Major Changes
		
 
• Updates based on nivolumab IB. Changed the requirement to collect amylase and lipase to amylase or lipase. Added amylase or lipase testing to follow up requirements.
 
• [REDACTED]
 
• the timing for PFS analysis was specified to be approximately around 6 months after last patient is randomized,
 
• dose modifications, criteria to resume treatment and discontinuation criteria were and safety algorithms were updated.
 

Revised Protocol 02(incorporates Amendment 10)	11-May-2016	
 
• Added a bullet to OS language in Section 8.1 and removed - from Section 8.4.5.2.
 

Revised Protocol 01 (incorporates Amendment 09 )	20-Apr-2016	
 
• [REDACTED]
 
• Clarified acceptable first line radiation treatment for patients with known brain metastasis and timing it must be completed prior to the start of study treatment.
 
• Updated guidance around the use of palliative radiation therapy during study treatment to better support standard practice in the community.
 
• Added guidance for dosing of subjects weighing less than 35kg. Clarified that dosing is not to be skipped in the presence of dose delays but resumed at the next time point.
 
• Clarified guidance for treatment beyond progression. Corrected timing of collection of screening procedures to be within randomization date rather than first treatment date as appropriate.
 
• Provided guidance on the collection of concomitant medications in the follow up setting.
 
• Provided definition of a SUSAR and how they will be reported.
 
• Provided detail on OS data to be provided to DMC
 

Original Protocol	07-Jul-2015	
 
• Not Applicable
 

## 2.5 Data Monitoring Committee

An independent Data Monitoring Committee (DMC) has been established to provide oversight of safety and efficacy considerations, study conduct, and risk-benefit ratio. Details of DMC responsibilities and procedures are specified in the DMC charter. Representatives of the Sponsor will serve only as coordinators of the committee, without having full member responsibilities or privileges. In addition, the Sponsor will independently review safety data in a blinded manner during the conduct of this trial to ensure that any safety issues are identified and addressed.

## 2.6 Blinded Independent Central Review (BICR)

A Blinded Independent Central Review (BICR) Committee will review tumor assessments to determine RECIST 1.1 response for the analyses of PFS, ORR and, DOR. PFS (per BICR) and ORR with DOR (per BICR), are secondary and exploratory endpoints for this study respectively. Details of the BICR responsibilities and procedures will be specified in the BICR charter.

## 3 OBJECTIVES

In subjects with ED-SCLC after completion of platinum-based first line chemotherapy:

### 3.1 Primary

- To compare OS of nivolumab in combination with ipilimumab versus placebo in subjects with ED-SCLC after completion of platinum-based first line chemotherapy.

### 3.2 Secondary

- To compare OS of nivolumab versus placebo in subjects with ED-SCLC after completion of platinum-based first line chemotherapy.
- To compare Blinded Independent Central Review (BICR) assessed PFS of nivolumab, and nivolumab in combination with ipilimumab, versus placebo
- To evaluate (descriptively) OS and BICR-assessed PFS of nivolumab combined with ipilimumab versus nivolumab
- To evaluate tumor mutational burden as a predictive biomarker for OS and PFS of nivolumab, and nivolumab in combination with ipilimumab

█ █

█ █

█ █

[REDACTED]

## 4 ENDPOINTS

### 4.1 Primary Endpoint

Overall Survival is defined as the time from randomization to the date of death. A subject who has not died will be censored on the last date the subject was known to be alive.

### 4.2 Secondary Endpoint(s)

Secondary endpoints will be evaluated at the same time as the OS primary endpoint analysis. The OS and PFS secondary endpoints comparing the experimental treatment groups with placebo will be tested hierarchically. The hierarchical order is defined in [section 7.5.3](#).

Secondary endpoint of OS comparing nivolumab monotherapy versus placebo is defined similarly to the primary endpoint.

[figure not shown]
Secondary endpoint PFS will be using PFS as assessed by BICR as primary analysis (sensitivity analysis of PFS will also be conducted using investigator assessment -see [Section 7.5.2.1](#)).

PFS is defined as the time from randomization to the date of first documented progression (per RECIST 1.1) as determined by BICR, or death due to any cause, whichever occurs first. Subjects who die without a reported progression (and die without start of subsequent therapy) will be

considered to have progressed on the date of their death. Subjects who did not have documented PD per BICR per RECIST1.1 criteria and who did not die will be censored on the date of their last evaluable tumor assessment on or prior to initiation of the subsequent anti-cancer therapy. Subjects who did not have any on study tumor assessments and did not die (or died after initiation of the subsequent anti-cancer therapy) will be censored on the randomization date. Subjects who started any subsequent anti-cancer therapy without a prior reported PD per BICR will be censored at the last evaluable tumor assessment on or prior to initiation of the subsequent anti-cancer therapy.

See Figure 4.2-1 for the graphical representation of this definition.

**Figure 4.2-1: Graphic Display of PFS Definition**

rand = randomization, STh = Subsequent Therapy

An OS descriptive analysis will be performed to evaluate nivolumab monotherapy versus nivolumab with ipilimumab treatment regimen. OS definition is similar to the primary endpoint.

Tumor Mutation Burden (TMB) is measured using FoundationOne CDx™ (F1CDx) assay, a comprehensive genomic profile (CGP) assay based on baseline tumor tissue. TMB is defined as

the number of somatic, coding, base substitution, and indel mutations per megabase of genome examined.

[REDACTED]

[REDACTED]

[REDACTED]

[REDACTED]

[REDACTED]

#### **4.3.4 Safety Endpoints**

Safety and tolerability will be measured by the incidence of deaths, adverse events, serious adverse events, adverse events leading to discontinuation, adverse events leading to dose delay, select adverse events and specific laboratory abnormalities (worst grade) in each treatment group. Toxicities will be graded using the National Cancer Institute (NCI) Common Terminology Criteria for Adverse Events (CTCAE) version 4.0. See details in the Core Safety SAP

#### **4.3.5 Pharmacokinetics**

Pharmacokinetic serum samples will be collected to characterize pharmacokinetics of nivolumab and to explore exposure-safety and exposure-efficacy relationships.

#### **4.3.6 Immunogenicity**

Blood samples for immunogenicity analysis will be collected from subjects assigned to the experimental treatment group(s) according to the protocol schedule. Samples will be evaluated for development of Anti-Drug Antibody (ADA) by a validated electrochemiluminescent (ECL) immunoassay.

#### **4.3.7 Outcomes Research**

Patients' overall health status will be assessed using the The EuroQol Group's self-reported health status measure (EQ-5D). EQ-5D essentially has 2 components- the EQ-5D descriptive system and the EQ visual analogue scale (EQ VAS). The EQ-5D descriptive system comprises

the following 5 dimensions: mobility, self-care, usual activities, pain/discomfort and anxiety/depression. Each dimension has 3 levels: no problems, some problems, severe problems. The EQ VAS records the subject's self-rated health state on a 100-point vertical, visual analogue scale (0 = worst imaginable health state; 100 = best imaginable health state).

## 5 SAMPLE SIZE AND POWER

Per original protocol, approximately 810 subjects were to be randomized to three treatment arms in a 1:1:1 ratio.

The primary objective is to compare OS of nivolumab in combination with ipilimumab versus placebo. The analysis of primary endpoint of OS will be conducted when at least 386 deaths have been observed pooled across the two treatment groups. With 386 events available for comparison of OS in nivolumab in combination with ipilimumab vs placebo, power of the log-rank test is approximately 90% to detect a hazard ratio (HR) of 0.72 with a type I error of 0.05 (two-sided). The critical hazard ratio for determining whether nivolumab in combination with ipilimumab is superior to placebo is 0.82.

Power calculations were performed using EAST® Software (version 6.4.1). Results were generated by 10000 simulations. Model assumptions were as follows:

Survival function for placebo arm was modeled using a four hazard pieces: OS rates at 3, 9, 18 and 26 months were assumed to be 90%, 47%, 15% and 9%, respectively, based on published survival curve for placebo maintenance in extensive-stage disease SCLC, adjusted for induction phase.

For nivolumab in combination with ipilimumab, a delayed effect versus placebo with a hazard ratio (HR) of 1 for the first 3 months and an HR of 0.68 thereafter was assumed, resulting into overall HR (experim over placebo) of 0.72 at time of the OS analysis, as determined from the 10000 simulations.

Median OS derived from the survival functions were 8.8 months and 11.0 months for the placebo and experimental treatment groups, respectively. Accrual information used in the simulations had the same pattern as the actual data at time of the protocol amendment (832 subjects were accrued in 28 months and randomized to the three treatment groups). A 5% probability of dropout by month 6 was taken into account. Given the observed accrual and dropout and survival assumptions it is expected that the duration of the study from start of randomization to analysis of OS will be approximately 35 months (28 months of accrual + 7 months of follow-up, providing an average follow up of 9 months).

The secondary endpoints of OS in nivolumab vs placebo and PFS in experimental treatments vs placebo will be tested hierarchically (see [Section 7.5.3](#)). Assuming 386 events are also available for comparison of OS in nivolumab vs placebo, power of the log-rank test is approximately 90% to detect a hazard ratio (HR) of 0.72 with a type I error of 0.05 (two-sided).

For PFS analyses comparing nivolumab or nivolumab in combination with ipilimumab vs placebo in all randomized subjects, 525 PFS events are projected to be observed at the time of

the OS analysis, which provides approximately 93% power to the log-rank test to detect an overall HR of 0.74 with a Type I error of 0.05 (two-sided). Piecewise exponential distributions were used to model PFS. The following assumptions were made: for the placebo group, a median PFS of 2 months and PFS rate at 12 months of 5% were assumed. Both experimental arms were assumed to have median PFS of 2 months (similar to placebo), with PFS rate at 12 months of 15%.

This study includes a sub-study to allow enrollment of patients from China (site-specific protocol Amendment 12). Data from these additional subjects will be reported separately. Subjects from China randomized on or before end of global study accrual will be included in the population used for the primary analysis clinical study report. The required number of deaths for the primary OS analysis is based on the global study population.

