8 STATISTICAL CONSIDERATIONS

8.1 Sample Size Determination

Per original protocol, approximately 810 subjects were to be randomized to the three treatment arms in a 1:1:1 ratio.

The primary objective is to compare Overall Survival (OS) of nivolumab in combination with ipilimumab versus placebo. The analysis of primary endpoint of OS will be conducted when at least 386 deaths have been observed pooled across the two treatment groups. Using accrual and treatment effect assumptions described below, it is expected that 208 events will be observed in placebo and 178 in nivolumab in combination with ipilimumab treatment groups. With 386 events available for comparison of OS in nivolumab in combination with ipilimumab vs placebo groups, power of the log-rank test is approximately 90% to detect a hazard ratio (HR) of 0.72 with a type I error of 0.05 (two-sided). The critical hazard ratio for determining whether nivolumab in combination with ipilimumab is superior to placebo is 0.82.

Power calculations were performed using EAST® Software (version 6.4.1). Results were generated by 10000 simulations. Model assumptions were as follows:

Survival function for placebo arm was modeled using a four hazard pieces: OS rates at 3, 9, 18 and 26 months were assumed to be 90%, 47%, 15% and 9%, respectively, based on published survival curve for placebo maintenance in Extensive-Stage SCLC, adjusted for induction phase³⁶. Median OS for placebo was 8.8 months.

For nivolumab in combination with ipilimumab, a delayed effect versus placebo with a hazard ratio (HR) of 1 for the first 3 months³⁷ and an HR of 0.68 thereafter was assumed, resulting into overall HR (experim vs placebo) of 0.72 at time of the OS analysis. Median OS for the experimental arm was 11.0 months.

Accrual information used in the simulations had the same pattern as the actual data at time of the protocol amendment (832 subjects were accrued in 28 months and randomized to the three treatment groups). A 5% probability of dropout by month 6 was taken into account. Given the observed accrual and dropout and survival assumptions it is expected that the duration of the study from start of randomization to final analysis will be approximately 35 months (28 months of accrual + 7 months of minimum follow-up, providing an average follow up of 9 months).

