#### **7.5.2 BICR Progression Free Survival**

BICR-assessed PFS for each of the two experimental arms will be compared to the control group using a two-sided log-rank test stratified by the same stratification factors as in the OS primary analysis. The secondary PFS endpoints will be tested hierarchically (see [Section 7.5.3](#)). If superiority of OS of nivolumab monotherapy over placebo comparison is not demonstrated, PFS is not tested

HRs and corresponding two-sided CIs will be estimated using a Cox proportional hazards model, with treatment group as a single covariate, stratified by the same stratification factors as in the OS primary analysis. Descriptive HR and corresponding two-sided 95% CI will be provided to evaluate differences between the two experimental arms.

PFS curves for each treatment group will be estimated using the KM product-limit method. Median PFS and corresponding two-sided, 95% confidence intervals will be computed.

PFS rates at 6, 9, 12, and 18 months will be estimated using KM estimates on the PFS curve for each treatment group. Minimum follow-up must be longer than the timepoint to generate the rate. Associated two-sided 95% CIs will be calculated.

The source of progression event (death versus progression) will be summarized by treatment group. The status of subjects who are censored in the PFS analysis will be tabulated for each treatment group using the following categories. This summary will be provided for all randomized subjects.

- On-study (on-treatment, in follow-up)
- Off-study (lost to follow-up, withdrawn consent, never treated)
- Received subsequent anticancer therapy

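### Do the SAP's 525 PFS events and 93% power conflict with the 386 deaths and 5% dropout assumed in the same section?

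*SAP*

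**What the plan says.** SAP Section 5 has two separate sets of assumptions.

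- **OS simulation.** Placebo OS is 90%, 47%, 15% and 9% at 3, 9, 18 and 26 months. The combination arm has a hazard ratio of 1 for three months and 0.68 afterwards. Accrual is 832 subjects in 28 months, with analysis near month 35. Here the SAP adds: "A 5% probability of dropout by month 6 was taken into account". Protocol Section 8.1 gives the expected split of the 386 deaths: "it is expected that 208 events will be observed in placebo and 178 in nivolumab in combination with ipilimumab treatment groups".
- **PFS projection.** For each comparison with placebo, "525 PFS events are projected to be observed at the time of" the cutoff for OS. The SAP then attaches a power to this count: "which provides approximately 93% power to the log-rank test to detect an overall HR of 0.74". The model is piecewise exponential. Placebo PFS has a median of 2 months and a 12-month rate of 5%. "Both experimental arms were assumed to have median PFS of 2 months (similar to placebo), with PFS rate at 12 months of 15" per cent. Dropout, cut points and the hazard after month 12 are not mentioned.

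SAP Section 4.2 ties the timing together: "Secondary endpoints will be evaluated at the same time as the OS primary endpoint analysis". For the secondary OS comparison, Section 5 says: "Assuming 386 events are also available for comparison of OS in nivolumab vs placebo, power of the log-rank test is approximately 90" per cent. That paragraph opens by stating that the secondary endpoints are tested hierarchically and points to Section 7.5.3. Section 7.5.2 repeats the gate: "If superiority of OS of nivolumab monotherapy over placebo comparison is not demonstrated, PFS is not tested".

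**The concern.** PFS is analysed at the OS cutoff, so its projected event count should rest on the same subjects, accrual and follow-up that produce 386 deaths. A count of 525 leaves only about 30 of the roughly 555 subjects in a comparison without an event, which seems few if 5% drop out by month 6. Uniform accrual with no dropout at all does give about 525 PFS events, but it also gives about 424 deaths. That suggests the two projections came from different settings.

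The quoted powers also stand alone in the text. PFS is tested only after two OS tests succeed, so a reader could take 93% as the chance of a PFS claim. These are the only figures for judging the formally tested PFS endpoints. At stake is whether stand-alone PFS power is overstated by about 3 points and whether the gating is hidden.

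**Working it through.** **Inputs from the documents:** the OS and PFS rates above; 832/3 = 277.3 subjects per arm, or 554.7 per comparison; accrual over 28 months with cutoff at month 35; 386 deaths; 5% dropout by month 6.

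**Assumptions needed because the SAP is silent:** one PFS cut at month 2; the last PFS hazard carried forward after month 12; cumulative accrual (t/28)^k, with k set to give 386 deaths; and a constant dropout hazard of −ln(0.95)/6 = 0.0085 per month, either continuing or stopping at month 6.

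**1. The stated figure.** Schoenfeld power is Φ(√(d/4)·|ln HR| − 1.96).

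- 525 events, HR 0.74: √131.25 × 0.3011 − 1.96 = 1.49, so 93.2%. The stated 93% is reproduced.
- 507 events, HR 0.74: √126.75 × 0.3011 − 1.96 = 1.43, so 92.4%. Losing 18 events costs 0.8 points.
- 386 events, HR 0.72: √96.5 × 0.3285 − 1.96 = 1.27, so 89.7%. The stated 90% for OS is reproduced.

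**2. PFS hazards.** Both arms have ln 2/2 = 0.347 per month to month 2. After that, placebo has ln(0.50/0.05)/10 = 0.230 and experimental ln(0.50/0.15)/10 = 0.120, a ratio of 0.52. The curves are not proportional, so the average hazard ratio depends on follow-up and on where the cuts fall.

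**3. Events and power at month 35.**

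| Dropout applied to | Accrual | Deaths | PFS events | Simulated PFS power |
|---|---|---|---|---|
| Neither | uniform | 424 | 526 | about 92% |
| Neither | slowed to match | 386 | 512–513 | not needed here |
| OS and PFS | matched | 386 (207 + 179) | about 507 | 89–90% |
| OS only | matched | 386 (207 + 179) | 519–522 | 90.5–91.9% |

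The last row follows Section 5 as it is laid out. It is 3 to 6 events below 525, that is 0.6% to 1.1%, at the stated number of deaths and close to the Protocol's 208 + 178 split. The first two rows remove dropout from OS, which contradicts the SAP, so they do not show that 525 and 386 conflict.

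**4. Late hazard.** Multiplying the unstated hazard after month 12 by 0.5 to 4 (an assumed range) gives 511–533 events with OS-only dropout, which contains 525. With dropout on both endpoints it gives 499–519.

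**5. Cut points.** An extra cut at month 6, keeping the stated medians and 12-month rates, changes power as follows. The month-6 PFS rates are assumed; dropout applies to PFS and accrual is matched.

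| Month-6 PFS, placebo / experimental | Power |
|---|---|
| 18% / 24% | about 75% |
| 20% / 30% | about 88% |
| 15% / 27% | about 90% |
| 20% / 35% | about 95% |

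The spread far exceeds the 3-point gap at issue, and one admissible shape exceeds 93% even with dropout.

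**6. Sequence.** Take both OS tests at 89.7% power and a correlation, from the shared placebo arm, between 178/386 = 0.46 and 0.50. The bivariate normal probability that both succeed is then about 83%. This is the ceiling for either PFS test under the SAP's own OS effects.

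**The case for a change.** The strongest reply is that dropout on OS only is not realistic. PFS counts death from any cause, so a subject lost to survival follow-up before progressing cannot later supply a PFS event. SAP Section 4.2 also censors PFS at subsequent anti-cancer therapy, so real PFS censoring should be heavier than OS dropout, not absent. On that view about 507 events is the better forecast. Even in the favourable settings, two-piece simulated power is about 91–92%, because 93% is a fixed-hazard-ratio value while the two-piece curves average nearer 0.75 at the matched follow-up.

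The modelling criticism stands: applying dropout to both endpoints would have been more coherent, and the PFS assumptions are under-described. It does not follow that the printed figures contradict the section's own inputs, because dropout is not among the PFS inputs. Nor does 89–90% follow as a correction. It rests on a single cut at month 2 that the SAP never states, and other shapes move power in both directions.

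On gating, the 83% ceiling is right under its assumptions and would be useful to a reader. But each figure is worded as the power of a log-rank test at two-sided 0.05, and the hierarchy is set out in Sections 5, 7.5.2 and 7.5.3. The primary OS 90% is ungated in any case.

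**Conclusion.** No change is needed. The event count, hazard ratio and power for PFS agree with one another (93.2% against a stated 93%), and 525 events can coexist with 386 deaths to within about 1% when dropout applies to OS only. If dropout also removes PFS follow-up, the shortfall is about 18 events (3.4%). That is 0.8 points of power at the stated hazard ratio, or about 3 points under a two-piece model. These results rest on power-law accrual, a cut at month 2 and a carried-forward late hazard, none of which the SAP states.

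Nothing in the trial turns on the difference. The analysis is triggered by deaths, the section reports 832 subjects already randomized, and alpha, test order and the method of analysis would be the same at 507 events as at 525. Stating the PFS dropout, cut points and late hazard, or adding a power figure for the sequence, would be optional reporting. It would not alter a decision or a conclusion.
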